# 7.1.2 Analysis Methods

# 7.1.2.1 Primary Efficacy Outcome

Determination of the primary efficacy outcome described in Section 7.1.1 utilizes a 3-step process:

1. A new episode of diarrhea: Participants are required to promptly report a new episode of diarrhea to trial site personnel (defined as > 3 unformed stools in 24 hours for 2 consecutive days). Additionally, surveillance for a new episode of diarrhea will include daily prompts to participants via a diary to record either the presence or absence of any unformed stool from Screening through Week 8. Thereafter participants will be required to contact the trial site if they experience a new episode of diarrhea between Week 8 and Week 24. At any time during the trial, if the number of unformed stools recorded in the diary by the participant meet the definition of a new episode of diarrhea, the trial site will be notified.

[figure not shown]
For each new episode of diarrhea (> 3 unformed stools in 24 hours for 2 consecutive days) during the trial period, a stool sample for central laboratory testing must be collected.

[figure not shown]
An Unscheduled Visit should be conducted with the participant if there is a positive laboratory stool test (Figure 7). A central laboratory test is a requirement for this trial and should not be replaced with a local laboratory test, unless under extenuating circumstances (e.g., central laboratory is closed due to pandemic). This sample should be collected before SOC CDI antibiotics are commenced.

- 2. **Investigator evaluation**: The onset of a new episode of diarrhea will trigger an Investigator evaluation for CDI. Investigator evaluation will include a) review of diarrhea data (> 3 unformed stools in 24 hours, for 2 or more consecutive days); b) assessment of stool *C. difficile* testing by central laboratory testing algorithm (Figure 7); and c) the clinical decision to start a course of SOC CDI antibiotics. Figure 8 outlines the possible outcomes of the Investigator evaluation process including the steps to be taken for cases where diarrhea does not meet the definition, but the Investigator has a strong clinical suspicion of *C. difficile*-related diarrhea.
- 3. Adjudication board: The determination of the Investigator evaluation prompts review of the event by an independent AB. The purpose of the independent AB is to is to confirm if the event is a CDI recurrence. The AB decision will be included in the dataset for the statistical analysis of the primary efficacy endpoint of the trial.

# Figure 7:Central Laboratory Testing Algorithm

Abbreviations: CDI = *Clostridioides difficile* infection; EIA = enzyme immunoassay; PCR = polymerase chain reaction.

#### 7.1.3 Stool Sample Analyses

Stool samples will be collected and analyzed as shown in the Schedule of Assessments (Table 3 and Table 4).

For the Qualifying CDI episode, a documented stool sample positive for toxigenic *C. difficile* is required within 45 days prior to Randomization to be eligible for the trial. Participants will be excluded if there is known testing on stool specimens that is positive for ova and/or parasite(s), or other enteric pathogens within 28 days prior to Screening.

Further stool samples will be collected at Screening while the participant is completing a course of SOC CDI antibiotics for the Qualifying CDI episode

for molecular testing, including but not limited to 16S rRNA gene amplicon sequencing, and safety testing.

On-trial stool samples will also be collected at scheduled trial visits. Analysis may also be performed at any other visit or time point (e.g., Unscheduled Visit, if any). On-trial stool samples will be collected before or after each scheduled trial visit. Participants may also be asked to provide a stool sample for unscheduled visits.

For each new episode of diarrhea (> 3 unformed stools in 24 hours for 2 consecutive days) during the trial period, a stool sample for central laboratory testing must be collected. A central laboratory test is a requirement for this trial and should not be replaced with a local laboratory test, unless under extenuating circumstances (e.g., central laboratory is closed due to pandemic). This sample should be collected before SOC CDI antibiotics are commenced.

Complete instructions for collection, handling, storage, and transportation/shipping of stool samples will be provided in a separate Laboratory Manual.

# 7.1.3.1 Stool and Blood Biomarkers

# 7.1.3.1.1 16S Ribosomal RNA Gene Amplicon Sequencing (Intestinal Microbiome Analysis)

# 7.1.3.2 Other Biomarkers

Biomarkers are objectively measured indicators of normal biological process, pathogenic, or pharmacologic response to a therapeutic intervention (FDA 2020; FDA-NIH Biomarker Working Group 2020).

7.1.4 Patient-Reported Outcomes

# 7.1.4.1 Participant Diary

		I
		5

# 7.2 Assessment of Safety and Adverse Events

#### 7.2.1 Adverse Events

The AE reporting period will begin at informed consent and will continue through the final follow-up visit or, in the case of withdrawal, until the outcome is determined. AEs will be assessed at each visit and through telephone contact with the participant. AEs will be coded using the Medical Dictionary for Regulatory Activities (MedDRA). AEs should be recorded on the CRF.

The primary clinical efficacy endpoint is CDI recurrence as defined by the independent AB. If during the Investigator Evaluation, the participant is suspected to have a *C. difficile*-related diarrhea in the trial, then CDI will not be recorded as an AE (unless this meets the criteria of a SAE); instead, it will be considered an on-trial *C. difficile*-related diarrhea and will be

included in the determination of efficacy. If the on-trial *C. difficile*-related diarrhea results in hospitalization of the participant, requiring an overnight stay, this will be recorded as an SAE and reported per the criteria for safety reporting.

# 7.2.2 Definition of Adverse Events

An AE is an untoward medical occurrence in a clinical investigation participant administered a pharmaceutical product and which does not necessarily have to have a causal relationship with this medicinal product. An AE can therefore be any unfavorable and unintended sign (including an abnormal laboratory finding, for example), symptom, or disease temporally associated with the use of the medicinal product, whether or not considered related to the medicinal product.

AEs may include, but are not limited to:

- Subjective or objective symptoms spontaneously offered by the participant and/or observed by the Investigator or medical staff.
- Findings at physical examinations.
- Laboratory abnormalities of clinical significance.

Disease signs, symptoms, and/or laboratory abnormalities already existing prior to the use of the IP are not considered AEs after treatment unless they reoccur after the participant has recovered from the pre-existing condition, or in the opinion of the Investigator, they represent a clinically significant exacerbation in intensity or frequency.

If clinically significant worsening from baseline is noted, the changes will be documented as AEs on the AE page of the CRF. Clinical significance is defined as any variation in signs, symptoms, or testing that has medical relevance and may result in an alteration in medical care. The Investigator will continue to monitor the participant until the assessment returns to baseline or until the Investigator determines that follow-up is no longer medically necessary.

Investigators should inform the Sponsor regarding any event that seems unusual, even if this event may be considered an unanticipated benefit to the participant.

# 7.2.3 Adverse Event Reporting

#### 7.2.3.1 Recording Adverse and Serious Adverse Events

The collection of AEs will begin from the time of informed consent of through the final trial visit. All AEs (serious and non-serious) should be recorded on the CRF.

Refer to Section 7.2.7 for definition and reporting requirement of SAEs. SAEs related to trial procedures after signing informed consent and before the first dose of CP101 shall also be reported.

# 7.2.3.1.1 Adverse Events Occurring Secondary to Other Events

In general, AEs occurring secondary to other events (e.g., cascade events or clinical sequelae) should be identified by their primary cause. For example, if severe diarrhea is

known to have resulted in dehydration, it is sufficient to record only what is considered the primary diagnosis, diarrhea, as the AE on the CRF and, if also serious, on the SAE form. However, medically significant AEs occurring secondary to an initiating event that are separated in time should be recorded as independent events on the CRF. For example, if a severe gastrointestinal hemorrhage subsequently leads to renal failure, both events should be recorded separately on the CRF.

# 7.2.3.1.2 Persistent or Recurrent Adverse Events

A persistent AE is one that extends continuously, without resolution between participant evaluation time points. Such events should only be recorded once in the CRF unless their severity increases. If a persistent AE becomes more severe, it should be recorded again on the AE CRF.

A recurrent AE is one that occurs and resolves between participant evaluation time points and subsequently recurs. All recurrent AEs should be recorded individually on the AE CRF.

# 7.2.3.1.3 Abnormal Laboratory Values

Clinically significant laboratory abnormalities will be recorded as AEs on the CRF and SAE form (if applicable).

If the clinically significant laboratory abnormality is a sign of a disease or syndrome (e.g., alkaline phosphatase and bilirubin  $5 \times$  upper limit of normal associated with cholecystitis), only the diagnosis (e.g., cholecystitis) needs to be recorded on the AE CRF and the SAE form (if applicable).

If the laboratory abnormality can be characterized by a precise clinical term, the clinical term should be recorded as the AE or SAE. For example, an elevated serum potassium level of 7.0 mEq/L should be recorded as "hyperkalemia."

Observations of the same clinically significant laboratory abnormality from visit to visit should not be repeatedly recorded as AEs on the CRF and SAE form (if applicable), unless their severity, seriousness, or etiology changes.

# 7.2.4 Solicitation of Specific Adverse Events

In addition to the collection of all AEs, the following AEs will be specifically solicited using a daily participant diary for 7 days following IP administration (Day 1 to Day 7): abdominal distention or bloating, chills/severe shivering, abdominal pain or cramping, increased diarrhea, constipation, nausea, vomiting, and fever. The diary will be reviewed at the Week 1 visit, and any AEs captured in the diary and confirmed by the Investigator will also be documented on the AE CRF page.

# 7.2.5 Assessment of Severity

The severity, or intensity, of an AE refers to the extent to which an AE affects the participant's daily activities. The severity of an AE will be evaluated according to the

National Cancer Institute Common Terminology Criteria for Adverse Events (NCI-CTCAE) version 5.0. The clinical significance of an AE is determined by the Investigator.

Changes in the severity of an AE should be documented in the CRF.

# 7.2.6 Assessment of Causality

The relationship of each AE to IP or trial intervention will be defined using the terms below.

Not Related (unrelated, not related, no relation) – The biology, time course between the administration of IP and the occurrence or worsening of the AE, or other factors rules out a causal relationship and/or another cause (concomitant drugs, therapies, complications, etc.) is suspected.

Related – The time course between the administration of IP and the occurrence or worsening of the AE is consistent with a causal relationship and no other cause (concomitant drugs, therapies, complications, etc.) can be identified. The definition implies a reasonable possibility of a causal relationship between the event and the IP. This means that there are facts (evidence) or arguments to suggest a causal relationship.

The following factors should also be considered:

- The temporal sequence from IP administration:
  - The event should occur after the IP is given. The length of time from IP exposure to event should be evaluated in the clinical context of the event.
- Underlying, concomitant, intercurrent diseases:
  - Each report should be evaluated in the context of the natural history and course of the disease being treated and any other disease the participant may have.
- Concomitant drug:
  - The other drugs the participant is taking or the treatment the participant receives should be examined to determine whether any of them might be recognized to cause the event in question.
- Known response pattern for this class of IP:
  - Clinical and/or preclinical data may indicate whether a particular response is likely to be a class effect.
- Exposure to physical and/or mental stresses
  - The exposure to stress might induce adverse changes in the recipient and provide a logical and better explanation for the event.
- The pharmacology of the IP
  - The known pharmacologic properties (absorption, distribution, metabolism, and excretion) of the IP should be considered.

**Note:** The Investigator's assessment of causality for individual AE reports is part of the trial documentation process and will be recorded in the participant's medical record, AE CRF, and on the SAE form if applicable. AEs recorded without the Investigator's assessment of the relationship to IP will be followed up until causality is assigned.

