# 7.2.7.2 Reporting Serious Adverse Events

[figure not shown]
Any AE that meets SAE criteria (Section 7.2.7) must be reported via EDC immediately (within 24 hours of knowledge by the Investigator). Regardless of causality, severity, and whether the participant has undergone any trial-related procedures, all SAEs must be reported and will be collected and recorded from the time the participant signs the consent form until 30 days following the final follow-up visit.

The initial report in the EDC should include at least the following information:

- Trial number
- Participant's identification number
- Description of the event
- Date and time of onset of the event
- Seriousness criteria
- Severity
- Investigator's assessment of Causality to the IP
- Participant's event outcome, as currently known

When additional information regarding an SAE is brought to the attention of the Investigator, this information should be entered into EDC. Examples would include but are not limited to the following:

- Signs and symptoms initially reported for which there is now a diagnosis leading to a change in the reported term
- Laboratory test results
- Outcome of the SAE
- Change in Investigator causality assessment due to results of further investigations

The Sponsor or designee will be responsible for ensuring Suspected Unexpected Serious Adverse Reaction are reported to IRBs/IEC per local requirements. These activities may be delegated by the Sponsor to their vendor and will be documented in the Safety Monitoring Plan.

Pregnancy in and of itself is not an SAE but all pregnancies should be reported in the same manner and timeframe as SAEs as described in Section 7.2.7. Complications of the pregnancy should be reported within 24 hours of knowledge by the Investigator (e.g., if the mother is hospitalized for dehydration) as an SAE. Pregnancies will be followed by the Sponsor to full term and beyond. Pregnancy terminations/abortions must be reported as an SAE.

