# 8.5.2 Adverse Events

Any AE reported on the CRF that occurs during or post the administration of IP is defined as TEAE. Additionally, it will be assumed that an AE that was reported to have started at Randomization (Day 1) without an associated onset time may have occurred after the administration of IP. Hence, AEs occurring at Randomization (Day 1) with no associated onset time are assumed to be treatment-emergent.

For the primary safety endpoint, the incidence rate of TEAEs will be presented by treatment group through Week 8.

For the other safety endpoints, the incidence rate of TEAEs and TESAEs will be presented by treatment group through Week 24.

In addition, an overview of TEAEs will be provided which summarizes the incidence of the following information:

- All TEAEs
- Drug-related TEAEs
- Maximum severity of TEAEs
- Deaths
- SAEs

The number and percentage of participants who experienced at least 1 TEAE will be presented by MedDRA system organ class and preferred term. Drug-related TEAEs, withdrawals due to TEAEs, and all SAEs will be summarized in the same manner.

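### Section 7.2.6 tests for Related more narrowly than the reasonable-possibility standard it claims to express, so drug-related TEAE counts can only be lowered

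*Protocol*

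**What the plan says.** Protocol Section 7.2.6 offers two categories and no intermediate one.

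- **Related** needs a time course consistent with causation and, in addition, that "no other cause (concomitant drugs, therapies, complications, etc.) can be identified". The paragraph then explains itself: "The definition implies a reasonable possibility of a causal relationship between the event and the IP", and "This means that there are facts (evidence) or arguments to suggest a causal relationship".
- **Not Related** applies when biology, timing or other factors "rules out a causal relationship and/or another cause (concomitant drugs, therapies, complications, etc.) is suspected".

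A list of factors to consider follows. It covers timing, underlying disease, class effects, stress and pharmacology. Concomitant drugs are also on it and "should be examined to determine whether any of them might be recognized to cause the event in question". An event without a causality assessment is followed up until one is assigned, so every event ends in one of the two categories.

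The classification is used in two places. Section 8.5.2 puts drug-related TEAEs in the TEAE overview and also tabulates them by system organ class and preferred term: "Drug-related TEAEs, withdrawals due to TEAEs, and all SAEs will be summarized in the same manner". Section 7.2.7.2 lists the "Investigator's assessment of Causality to the IP" among the minimum contents of the initial SAE report.

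**The concern.** A reasonable possibility means that something points to the product. It does not mean that everything else has been excluded. The first sentence of the Related definition asks for that exclusion, and the Not Related definition reaches its result on mere suspicion of an alternative. The operative test is therefore narrower than the standard the paragraph says it expresses.

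In this trial competing explanations will often be at hand. Participants have just had a CDI episode and 10 to 21 days of CDI antibiotics (Section 3.1). Six of the eight solicited event terms in Section 7.2.4 are gastrointestinal, and Section 1.5.2 reports that gastrointestinal symptoms were the most frequent treatment-related events in PRISM3. The conflict thus falls on the events that matter most for the product's tolerability profile.

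At stake are the absolute level of the drug-related summaries and consistent classification across about 100 sites. Causality is a two-way field set at the site, so later analysis cannot recover events that were classed Not Related only because another cause was suspected.

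**Working it through.** No figure in the plan depends on this point, so the check sets the sentences side by side. Take events whose timing is consistent with the product and apply each sentence in turn.

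| Event | Related: no other cause identified? | Not Related: ruled out, or other cause suspected? | Reasonable possibility? |
|---|---|---|---|
| A. Evidence for the product, no other cause in view | met | not met | yes |
| B. Evidence for the product, another cause identified | fails | met | yes |
| C. Evidence for the product, another cause suspected but not identified | met | met | yes |
| D. Causal link ruled out | not applicable | met | no |

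- A and D are classified alike on every reading.
- B is classed Not Related although it meets the stated standard.
- C satisfies both category definitions, because one turns on *identified* and the other on *suspected*. Two Investigators could classify the same event differently and both follow the text.

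The factor list does not repair B or C. Looking for other drugs or diseases that might explain the event is proper. Under the operative wording, though, each alternative found stops being something to weigh and becomes disqualifying.

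**Direction.** Let R be the events with a reasonable possibility and O the events that the operative test calls Related. By the definition's own statement, an event that passes the operative test carries a reasonable possibility, so O lies within R and the count of O cannot exceed the count of R. The count falls whenever a B event occurs, or a C event is resolved to Not Related. The same holds for the number of participants with at least one such event.

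**Size.** This cannot be derived. It would need the share of reasonably possible events that have a competing cause, and how those events cluster within participants. The protocol gives neither.

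**The case against.** The strongest reply is that the reasonable-possibility sentence is a gloss on the sentence before it and not a second rule. Every event admitted by the first sentence does carry a reasonable possibility, so the two are not logically incompatible. That is correct, and the defect is best described as a test narrower than its stated standard. It does not remove the problem: the standard also covers B events, which the test excludes, and the triggers still overlap for C events.

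The objection also limits what may be inferred:

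- *That the primary safety result is affected.* It is not. The primary safety endpoint is the incidence of all TEAEs through Week 8, and TEAEs and TESAEs through Week 24 are likewise counted without regard to relatedness (Section 8.5.2).
- *That CP101 is made to look safer than placebo.* One rule applies to both arms, and Investigators stay blinded until Week 24 (Section 3.4.2). No difference between arms is built in.
- *That expedited reports will be suppressed.* Section 7.2.7.2 sends every SAE to the Sponsor within 24 hours whatever its causality. No section says that the Investigator's opinion alone decides whether a serious event is a suspected unexpected reaction. This is a possible risk only.
- *That the loss can be sized from PRISM3.* A reader might scale down the 16.3% drug-related TEAE rate on CP101 in Section 1.5.2 by an assumed share of events with another cause. The protocol gives no such share and does not state the PRISM3 causality definition. The 16.3% also reads as a proportion of participants, and a participant leaves the numerator only if all of their related events are reclassified.
- *That almost every gastrointestinal event would be lost.* PRISM3 Investigators did attribute such events to treatment after CDI antibiotics, under whatever rule applied there. Suspected on-trial *C. difficile*-related diarrhea is also not recorded as an AE unless serious (Section 7.2.1), which takes the most obvious competing diagnosis largely out of the non-serious count.

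**Conclusion.** The point holds in a limited form. The Related condition and the Not Related trigger in Section 7.2.6 are both narrower than the reasonable-possibility standard the definition claims, and their triggers leave some events in both categories. Followed as written, events with a plausible product contribution and a competing explanation are classed Not Related, which lowers absolute drug-related TEAE counts in both arms. The direction follows from the wording. The size is unknown and could be small if Investigators apply the gloss instead of the operative sentence.

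This should be corrected, since the loss occurs when the Investigator assigns causality and the statistical analysis plan cannot undo it.

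**What to change.** Make one standard operative in Section 7.2.6 and in the CRF guidance:

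- Define Related as a reasonable possibility that the IP caused or contributed to the event, whether or not another possible cause exists.
- Define Not Related as the absence of such a possibility.
- Delete the condition that no other cause be identifiable, and delete the suspected-other-cause trigger from Not Related.
- Keep underlying disease, concomitant drugs and other alternatives only in the list of factors to weigh.

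The two categories then no longer overlap, and every event falls in exactly one.

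The cost is a wording change in the protocol and the matching CRF guidance. No dose, treatment rule or efficacy analysis changes. Reported drug-related rates may rise in both arms, which is a small downside.
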